| 12.7 Appendix 7. Hepatotoxicity Stopping Rules: Suggested Actions and Follow-up Assessments | 71 |
| 12.8 Appendix 8. Six Minute Walk Test Instructions..... | 75 |
| 12.9 Appendix 9. Six Minute Walk Test Recording Form..... | 77 |

List of Tables

| | |
|---|----|
| Table 2-1. Schedule of Activities..... | 11 |
| Table 5-1. Ivabradine Dose Titration at Day 15 Based on Heart Rate From Electrocardiogram | 17 |
| Table 7-1. Study Treatment..... | 22 |
| Table 12-1. Analyte Listing | 45 |
| Table 12-2. Conditions for Withholding and/or Permanent Discontinuation of Amgen Investigational Product and Other Protocol-required Therapies due to Potential Hepatotoxicity..... | 72 |

List of Figures

| | |
|---|----|
| Figure 12-1. Sample Electronic Serious Adverse Event Contingency Report Form..... | 58 |
| Figure 12-2. Sample Pregnancy and Lactation Notification Worksheets | 67 |

1. Protocol Synopsis

Protocol Title: Open-label, Single-arm Study Assessing the Efficacy and Safety of Ivabradine (Corlanor) in African-American/Black Subjects With Heart Failure and Left Ventricular Systolic Dysfunction

Short Protocol Title: A Phase 4 Study of Ivabradine in African-American/Black Subjects with Heart Failure and Left Ventricular Systolic Dysfunction

Study Phase: 4

Indication: Heart Failure (HF)

Rationale

The goal of this study is to determine the impact of adding ivabradine therapy to the standard of care (SOC) in African-American/Black subjects with HF and reduced ejection fraction (HFrEF) on changes in heart rate (HR) from baseline (SOC alone). Changes in HR from baseline will be correlated with the changes from baseline in activity level of the subjects, as measured by both a standard 6-minute walk distance and an accelerometer device.

Objective(s)/Endpoint(s)

| Objectives | Endpoints |
|---|--|
| Primary | |
| 
Determine whether ivabradine effectively reduces HR from baseline to day 57 in African-American/Black subjects. | 
Change in HR from baseline to day 57 |

Hypotheses

The primary hypothesis is that ivabradine effectively reduces HR between baseline and day 57 in African-American/Black subjects. Because mean reductions of approximately 5 beat per minute (bpm) have been observed in the overall placebo-treated subjects in the SHIFT study as well as in the placebo-treated subjects of the subgroup analysis of non-African-American/Black subjects enrolled in the SHIFT study, we will test whether the mean reduction with ivabradine exceeds 5 bpm, and estimate the degree to which the mean reduction with ivabradine exceeds 5 bpm.

Overall Design

This study is a prospective, open-label, single-arm intervention study in African-American/Black subjects with HFrEF.

There will be a 7-day screening period, a 57-day open-label treatment period, and a safety follow-up at day 87 or 30 days after the last administration of the investigational product.

Number of Subjects

Approximately 30 to 100 subjects

Summary of Subject Eligibility Criteria

Subjects will be male or female ≥ 18 years of age, describing self as African-American/Black, with a diagnosis of HF confirmed by medical records, in stable condition, and treated with stable optimal pharmacological therapy. Subjects must also have left ventricular ejection fraction (LVEF) $\leq 35\%$ confirmed prior to enrollment, New

York Heart Association class II to IV, and electrocardiogram documentation at the time of screening of sinus rhythm with resting HR \geq 70 bpm.

For a full list of eligibility criteria, please refer to [Section 6.1](#) to [Section 6.2](#).

Treatments

The starting dose of ivabradine is 5 mg twice daily (BID). In subjects with a history of conduction defects, or in subjects in whom bradycardia could lead to hemodynamic compromise, therapy is to be initiated at 2.5 mg BID based on investigator discretion. At the day 15 visit, the dose will be titrated according to HR as defined in the table below. Ivabradine dose levels can be adapted to HR at any clinical visit if necessary.

| | Initial Dose: 5 mg BID | Initial Dose: 2.5 mg BID |
|---|------------------------|--------------------------|
| HR \geq 60 bpm | 7.5 mg BID | 5.0 mg BID |
| HR \geq 50 bpm, < 60 bpm | 5.0 mg BID | 2.5 mg BID |
| HR < 50 bpm and/or signs or symptoms of bradycardia | 2.5 mg BID | Discontinue therapy |

Abbreviations: BID = twice daily; bpm = beats per minute; HR = heart rate

Procedures

There will be a 7-day screening period that will allow accurate measurement of baseline activity as measured by the accelerometer. On day 1, eligible subjects with confirmed sinus rhythm and HR \geq 70 bpm will be enrolled into a 57-day open-label treatment period. A safety follow-up will be conducted at day 87 or 30 days after the last administration of the investigational product.

For a full list of study procedures, including the timing of each procedure, refer to [Section 9.2](#) and the Schedule of Activities in [Section 2.2](#).

Statistical Considerations

The primary analysis for this study will be performed when all subjects have completed all planned study procedures. This primary analysis will evaluate the effect of ivabradine on HR reduction at day 57 in African-American/Black subjects overall (the primary endpoint). Descriptive statistics of the exploratory endpoints will be summarized. Safety data will be tabulated.

Efficacy analyses will be performed on the full analysis set (FAS), which includes all enrolled subjects.

Safety analyses will be performed on the safety analysis set (SAS), which includes all enrolled subjects who receive at least 1 dose of investigational product on study.

[figure not shown]
Efficacy analyses of the primary endpoint will test whether the mean reduction with ivabradine exceeds 5 bpm. Summary statistics and least-square means along with 95% confidence interval, analyzed by the repeated-measures linear model, will be provided for the primary endpoint.

For a full description of statistical analysis methods, please refer to [Section 10](#).

Sponsor Name: Amgen Inc.

2. Study Schema and Schedule of Activities

2.1 Study Schema

Abbreviations: BID = twice daily; IP = investigational product

2.2 Schedule of Activities

Table 2-1. Schedule of Activities

| Procedure | Screening Period | Treatment Period (Days) | | | | Safety Follow-Up Period/ Early Termination Visit ^a (Phone Contact for Safety Follow-up only) |
|---|--------------------|-------------------------|---|-----------------|-----------------|--|
| | Screening (7 days) | Day 1 ± 2 days | Day 15 ± 2 days (dose titration begins) | Day 29 ± 2 days | Day 57 ± 5 days | Day 87 or 30 days after the last dose of open-label IP |
| Informed consent | X | | | | | |
| Full physical examination | X | | | | X | |
| Physical measurements ^b (height and weight) | X | | | | | |
| Medical history ^c | X | | | | | |
| Demographics ^d | X | | | | | |
| Vital signs ^e | X | X | X | X | X | |
| 12-lead ECG | X | X | X | | X | |
| Laboratory assessments | X | | | | | |
| Pregnancy test (urine) in women of childbearing potential only | X | X ⁱ | | | | |
| Adverse event collection/ recording/reporting | X ^f | X | X | X | X | X |
| Serious adverse event collection/recording/reporting ^f | X | X | X | X | X | X |

Footnotes defined on next page

Table 2-1. Schedule of Activities

| Procedure | Screening Period | Treatment Period (Days) | | | | Safety Follow-Up Period/ Early Termination Visit ^a (Phone Contact for Safety Follow-up only) |
|---|--------------------|-------------------------|--|-----------------|-----------------|--|
| | Screening (7 days) | Day 1 ± 2 days | Day 15 ± 2 days (dose titration begins) | Day 29 ± 2 days | Day 57 ± 5 days | Day 87 or 30 days after the last dose of open-label IP |
| Disease-related event collection/ recording/reporting | | X | X | X | X | X |
| Vital status | | | | | | X |
| Concomitant medications | X | X | X | X | X | X |
| 6-Minute walk test (6MWT) | | X | | | X | |
| Accelerometer ^g | X | X | X | X | X | X ⁱ |
| Investigational product ^h | | X | X | X | X | |

Page 2 of 2

Abbreviations: 6MWT = 6-Minute walk test; ECG = electrocardiogram; IP = investigational product

^a If a subject discontinues the study, the subject must return to the study clinic in 30 days after discontinuation.

^b Height in centimeters should be measured without shoes. Weight in kilograms should be measured without shoes.

^c Medical history will include substance usage (eg, alcohol, tobacco, and caffeine).

^d Demographics will include sex, age, race and ethnicity.

^e Vital signs will include systolic/diastolic blood pressure, heart rate, respiratory rate, and temperature. Subject must be in a supine position in a rested and calm state for at least 5 minutes before blood pressure assessments are conducted. If the subject is unable to be in the supine position, the subject should be in most recumbent position as possible. The position selected for a subject should be the same that is used throughout the study and documented on the vital sign case report form (CRF).

^f Adverse events related to any study procedures/study activity are collected, recorded, and reported from signing of the informed consent. All other adverse events including disease related events (DREs) are collected, recorded, and reported from day 1 (from first dose of investigational product). Serious adverse events are collected, recorded, and reported from signing of the informed consent through 30 days after the last dose of IP or end-of-study/safety follow-up visit, whichever is later.

^g A 7-day screening with the accelerometer is required before day 1 dosing. The subjects will be instructed to wear the accelerometer every day except to be recharged. The accelerometer is to be worn daily from screening through the end of treatment period (day 57).

^h On day 1, ivabradine will be dosed in the clinic and then will be dispensed at each study visit. At each clinic visit, the subject is to return investigational product for accountability. On day 15, dose titration will begin (7.5 mg twice daily [BID]) and subjects will begin to take ivabradine at home. The last dose of ivabradine will be taken on day 57.

ⁱ If screening pregnancy test is done ≥ 7 days from day 1, a repeat pregnancy test will be done on day 1 prior to dosing.

^j If a subject discontinues from the study, the accelerometer and investigational product is to be returned to the study clinic.

3. Introduction

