5.1 Overall Design

Currently, there are no data available on the efficacy of ivabradine to reduce HR in African-American/Black subjects with HFrEF, due to the fact that the pivotal outcome study, SHIFT, was conducted outside of the US ([Swedberg, et al, 2010](#)).

African-American/Black subjects have a significantly higher prevalence of HF and generally experience worse outcomes than Caucasians ([Yancy et al, 2013](#)).

Considering the absence of representation of African-American/Black subjects with HFrEF in SHIFT and the potential limitations of β -blockade in that population, as described above, the primary objective of this study is to assess the efficacy of ivabradine in reducing HR in that population on top of optimal SOC.

As exploratory endpoints, [REDACTED]

This study is a prospective, open-label, single-arm intervention study in African-American/Black subjects with HFrEF. Approximately 30 to 100 subjects will be enrolled to receive ivabradine in an open-label design.

Eligible subjects will include African-American/Black subjects with chronic HFrEF, New York Heart Association (NYHA) classes II to IV, with baseline HR \geq 70 bpm in sinus rhythm and a left ventricular ejection fraction (LVEF) \leq 35% who are on stable (\geq 4 weeks) optimal HF therapy, including maximally tolerated dose of β -blockers.

After signing the informed consent form, subjects will enter a 7-day screening period that will allow accurate measurement of baseline activity as measured by the accelerometer (which is a non-Amgen, medical device). On day 1, eligible subjects with confirmed sinus rhythm and HR \geq 70 bpm will be enrolled into a 57-day open-label treatment period. The starting dose of ivabradine is 5 mg twice daily (BID). In subjects with a history of conduction defects, or in subjects in whom bradycardia could lead to hemodynamic compromise, therapy is to be initiated at 2.5 mg BID, based on investigator discretion. On day 15, the dose will be titrated according to HR as defined in [Table 5-1](#). Ivabradine dose levels can be adapted to HR at any clinical visit if necessary.

Table 5-1. Ivabradine Dose Titration at Day 15 Based on Heart Rate From Electrocardiogram

| | Initial Dose: 5 mg BID | Initial Dose: 2.5 mg BID |
|---|------------------------|--------------------------|
| HR ≥ 60 bpm | 7.5 mg BID | 5.0 mg BID |
| HR ≥ 50 bpm, < 60 bpm | 5.0 mg BID | 2.5 mg BID |

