| HR < 50 bpm and/or signs or symptoms of bradycardia | 2.5 mg BID | Discontinue therapy |

Abbreviations: BID = twice daily; bpm = beats per minute; HR = heart rate

A safety follow-up will be conducted at day 87 or 30 days after the last administration of the investigational product.

The overall study design is described by a study schema in [Section 2.1](#). The endpoints are defined in [Section 4.1](#).

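### Footnote h of the Schedule of Activities misstates Day 15 dosing: it gives 7.5 mg BID without the Table 5-1 conditions and starts home dosing on Day 15 instead of Day 1

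*Protocol*

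**What the plan says.** Footnote h of Protocol Table 2-1 (Section 2.2) opens with "On day 1, ivabradine will be dosed in the clinic and then will be dispensed at each study visit". It continues: "On day 15, dose titration will begin (7.5 mg twice daily [BID]) and subjects will begin to take ivabradine at home". The visit columns of the same table run "Day 1 ± 2 days | Day 15 ± 2 days (dose titration begins) | Day 29 ± 2 days", so nothing is scheduled between Day 1 and Day 15.

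The titration rule is set out elsewhere:

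- Synopsis, Treatments: "At the day 15 visit, the dose will be titrated according to HR as defined in the table below".
- Table 5-1 in Section 5.1, where the first dose column is for 5 mg BID starters and the second for 2.5 mg BID starters. Its top row is "HR ≥ 60 bpm | 7.5 mg BID | 5.0 mg BID". In the middle band, from 50 up to but not including 60 bpm, each group simply stays on its starting dose. The bottom row is "HR < 50 bpm and/or signs or symptoms of bradycardia | 2.5 mg BID | Discontinue therapy".
- Section 5.1 also allows later changes: "Ivabradine dose levels can be adapted to HR at any clinical visit if necessary".
- Sections 5.4 and 7.4 refer to Table 5-1. Section 7.4.2.1 allows an increase, no change or a decrease on Day 15, guided by Table 5-1 and the investigator's judgment, and names 7.5 mg BID as the maximum.
- SAP Table 3-1 repeats Table 5-1.

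Section 9.1.2 says that ivabradine is given at each visit as the Schedule of Activities sets out. Section 7.6 has subjects bring back bottles and leftover tablets for counting at each visit.

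**The concern.** A footnote on the study-drug row is a dosing instruction. This one attaches the highest dose to Day 15 and leaves out every condition on which that dose depends. The subjects most exposed would be those whose heart rate has already fallen below 60 bpm, those with bradycardia symptoms, and those started on 2.5 mg BID because of conduction defects or because bradycardia could compromise them hemodynamically.

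The home-dosing phrase conflicts with the footnote's own first sentence and with BID dosing from Day 1. Read literally, it leaves most of the first two weeks without a way to take the drug.

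Section 9 requires adherence to the Schedule of Activities, and Section 9.1.2 directs sites to it for giving ivabradine. A mistake there is therefore more than a slip in background text.

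**Working it through.** **1. Dose: footnote h against Table 5-1.** Suppose the footnote is read literally, as 7.5 mg BID on Day 15. The difference per dose is 7.5 mg minus the Table 5-1 dose.

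| Day 15 finding | Started on 5 mg BID | Started on 2.5 mg BID |
|---|---|---|
| HR 60 bpm or more | 7.5 − 7.5 = 0 | 7.5 − 5.0 = +2.5 mg |
| HR 50 to below 60 bpm | 7.5 − 5.0 = +2.5 mg | 7.5 − 2.5 = +5.0 mg |
| HR below 50 bpm, or bradycardia signs or symptoms | 7.5 − 2.5 = +5.0 mg | 7.5 mg where the rule is to stop |

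The footnote matches 1 of 6 cells. Cells are not frequencies, and the documents give none. As an illustration only, take the planning mean reduction of 13 bpm (Protocol Section 10.1, a 28-day figure applied here to Day 15). A subject entering at the 70 bpm minimum would reach 70 − 13 = 57 bpm, where a 5 mg starter stays on 5 mg BID. A subject entering at 77 bpm, the SAP Section 4.2 subgroup cut, would reach 77 − 13 = 64 bpm, where 7.5 mg BID is correct for a 5 mg starter. So 7.5 mg BID may be common, but it cannot be assumed for everyone.

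**2. How long a wrong dose could last.** The next scheduled visit after Day 15 (± 2) is Day 29 (± 2).

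- Nominal: 29 − 15 = 14 days.
- Shortest: (29 − 2) − (15 + 2) = 10 days.
- Longest: (29 + 2) − (15 − 2) = 18 days.

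Day 29 has vital signs, which include heart rate, but no ECG in Table 2-1. The title of Table 5-1 specifies heart rate from ECG. Section 5.1 nevertheless allows the dose to be adapted to heart rate at any clinical visit, so correction on Day 29 is possible.

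**3. Home dosing.** Dosing is BID from Day 1 (Section 5.1, Table 7-1). Assume two doses on Day 1, one of them in the clinic. Doses before the Day 15 visit, less the one clinic dose:

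- Visit on Day 15: 14 × 2 = 28, and 28 − 1 = 27 outside the clinic.
- Visit on Day 13: 12 × 2 = 24, and 24 − 1 = 23 outside.
- Visit on Day 17: 16 × 2 = 32, and 32 − 1 = 31 outside.

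If Day 1 has only the clinic dose, the nominal count is 28 − 1 = 27 doses, of which 26 are outside. On any of these counts home dosing has to start right after the Day 1 visit.

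**4. Planning figures.** The footnote does not enter the power calculation, and that figure reproduces. In a two-sided one-sample t-test at 0.05, with difference 13 − 5 = 8 bpm and SD 10.4 bpm, 10% dropout takes 30 to 27 subjects and 100 to 90. Noncentral-t power is 97.0% for 27 and above 99.9% for 90, against the stated range of about 97% to above 99%.

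**The case against.** The strongest reply is that the rule is not in doubt. The footnote says that titration begins; it does not say that every subject receives 7.5 mg BID. The figure plausibly stands for the maximum dose in Section 7.4.2.1, and the at-home phrase may refer to the titrated dose. The same schedule requires an ECG on Day 15, which is the input to Table 5-1. Footnote h gives no starting dose, so a site cannot dose from it alone. To start a subject on 2.5 mg BID, a site would have used the synopsis or a dosing section, each of which ties titration to the HR-based table. Section 9 does not rank the schedule above the dosing sections.

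Most of this stands, and it makes the risk small. It does not make the sentence correct: the footnote does not say that 7.5 mg is a maximum, or that the at-home phrase concerns only the titrated dose. Section 9.1.2 still points to this table for giving the drug.

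A reader might infer more than the documents support:

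- *The protocol has two competing titration rules.* It does not. All the dedicated dosing sections and SAP Table 3-1 agree.
- *The footnote orders an overdose.* It does not. 7.5 mg BID is a permitted dose, so the error would be one of titration.
- *Subjects go without drug from Day 2 to Day 14.* The dispensing, BID and tablet-return provisions contradict this.

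**Conclusion.** Footnote h is wrong on both counts: it omits the conditions on the 7.5 mg BID dose, and it dates home dosing from Day 15. The intended rule is clear from the rest of the protocol and the SAP, so the practical risk is limited to wrong titration at a site that relies on the footnote.

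The literal footnote matches 1 of 6 Table 5-1 cells. A wrong Day 15 dose could be corrected on Day 29, nominally 14 days later (10 to 18 days with visit windows). About 27 of the first 28 doses fall outside the clinic, assuming two doses on Day 1 with one in clinic. The number of subjects who would be misdosed cannot be estimated from the documents. A reader might look for an effect on the primary analysis; none follows, because no sample size, power or analysis figure depends on this sentence.

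**What to change.** Replace the Day 15 sentence in footnote h with:

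> Starting after the Day 1 in-clinic dose, subjects take ivabradine BID at home between visits, with dosing at study visits per Section 9.1.2. On Day 15 the dose is increased, kept or reduced, or ivabradine is discontinued, per Table 5-1 and Section 7.4.2.1, based on ECG HR, signs or symptoms of bradycardia, starting dose and investigator judgment (maximum 7.5 mg BID).

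The wording names bradycardia symptoms and investigator judgment because Table 5-1 and Section 7.4.2.1 make the dose depend on them. It keeps dosing at visits so that it agrees with Section 9.1.2.

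The cost is one sentence and a clarification to the 1 to 3 sites in Section 5.2.2. Visits, sample size and analysis stay as they are.

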3.1 Study Rationale

The goal of this study is to determine the impact of adding ivabradine therapy to the standard of care (SOC) in African-American/Black subjects with heart failure (HF) and reduced ejection fraction (HFrEF) on changes in heart rate (HR) from baseline (SOC alone). Changes in HR from baseline will be correlated with the changes from baseline in activity level of the subjects, as measured by both a standard 6-minute walk distance and an accelerometer device.

3.2 Background

3.2.1 Disease

Chronic heart failure (HF) is a syndrome that results in inadequate systemic blood flow when normal neurohormonal mechanisms, namely, the sympathetic nervous system and the renin-angiotensin-aldosterone system, are exhausted or overwhelmed and are no longer able to deliver an adequate physiological response. While several interventions including angiotensin-converting-enzyme inhibitors (ACEi), beta (β)-blockers, aldosterone antagonists, coronary revascularization, and biventricular pacing ([Jessup and Brozena, 2003](#)) have been shown to improve symptoms, reduce the rate of HF hospitalizations, and improve mortality, both mortality and morbidity related to HF remain high. Chronic HF is associated with repeated hospitalizations, substantially reduced quality of life, a yearly mortality rate in the United States of 7.5% ([Webster et al, 2006](#)), and approximately 5.1 million persons in the US clinically manifest symptoms of chronic HF ([Go et al, 2013](#)). The etiology of chronic HF in adults is primarily myocardial dysfunction secondary to ischemic heart disease, usually as a consequence of coronary artery disease and myocardial infarction, although hypertensive cardiomyopathy is prevalent in African-American/Black subjects ([Yancy et al, 2013](#); [McMurray et al, 2012](#)).

Observational and interventional studies in adults demonstrate that relatively high resting HR is not only a biomarker correlated with poor clinical outcomes, but is also a validated surrogate marker and a modifiable risk factor for chronic HF ([Swedberg et al, 2010](#); [McAlister et al, 2009](#); [Flannery et al, 2008](#); [Lechat et al, 2001](#)). Recently reported data from registries and clinical studies suggest that more than half the patients with HF receiving β -blockers will nevertheless have a resting HR > 70 beats per minute (bpm) ([Maggioni et al, 2012](#); [Maggioni et al, 2010](#)). The ability to achieve further HR reduction

beyond what is achieved with β -blockers would therefore constitute a significant therapeutic advance.

Racially diverse populations may exhibit differences in drug response that may be due, in part, to variations in gene sequences. Functional single-nucleotide polymorphisms (SNPs) are common in the genes encoding β -adrenergic receptors (adrenergic receptors alpha2A, as well as beta-1 and beta-2-adrenergic receptor), and in a gene that regulates the response of these receptors to catecholamines, the G-protein receptor kinase 5 (*GRK5*) (Liggett et al, 2006; Liggett et al, 2008). Importantly, both the β -1 adrenergic receptor (*ADRB1*) Arg389 > Gly and the *GRK5* Gln41>Leu SNPs are over-represented in African-American/Black subjects. The *ADRB1* Arg389>Gly SNP is found in about 42% of African-American/Black and 27% of Caucasians, and the distribution of the *GRK5* Gln41 > Leu SNP shows even more ethnic divergence, as it is found in about 33% of African-American/Black but only 1% of Caucasians (Moore et al, 1999; Liggett et al, 2008). Both SNPs result in a blunted response of the β -adrenergic receptor to catecholamines and may therefore affect individual clinical responses to β -blockers in patients with HF (Liggett et al, 2006; Liggett et al, 2008).

